Subjects with cirrhosis (see [Section 7.5.4](#)) and classified as Child-Pugh Class B or Child-Pugh Class C will follow a modified dosing regimen, initiating 5 mg OCA or matching placebo once weekly. After a minimum of 3 months dosing once weekly with 5 mg OCA or matching placebo, and following review of the pre-titration laboratory results to assess safety and tolerability, the dosing frequency of 5 mg OCA or matching placebo should be increased to twice weekly (at least 3 days apart). Subjects who have maintained the twice weekly dosing frequency for a minimum of at least 6 weeks and meet the dose titration criteria should up-titrate to the maximum allowed dose of 10 mg OCA or matching placebo twice weekly.

Investigators may decrease the dosing frequency (back to once weekly) or dose for any subject at any time during the study, as considered clinically appropriate (eg, tolerability).

The dosing regimen should be determined as described shown in [Table 13](#). Investigators should follow the dosing/titration schedule as shown described in [Section 7.4](#) and [Appendix A](#).

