Dose Titration due to Change in Cirrhosis or Child-Pugh Score - When subjects demonstrate a change in cirrhosis status (as assessed per Section 7.5.4) or Child-Pugh Score (Section 7.5.5) dosing should be reassessed and the dosing regimen modified appropriately. Changes in Child-Pugh Score that result from a transient, explainable change in laboratory parameters should be documented appropriately, and should not necessarily result in a change to the dosing regimen. Dosing should follow the titration schedule of the new dosing regimen such that the maximum dose within that dosing regimen is ultimately attained, based on tolerability, biochemical response, and clinical judgment.

Subjects who exhibit development of cirrhosis at any point in the study should be assessed per Section 7.5.4. If the presence of cirrhosis is confirmed and the subject's Child-Pugh score is either B or C, the appropriate modified dosing regimen should be followed. The dose or frequency of investigational product should be down-titrated to the next lowest dosing frequency in the appropriate modified dosing regimen unless the subject is currently taking a dose and frequency also specified in the modified dosing regimen and the Investigator determines that it is clinically appropriate for the subject to continue at that dose (Appendix A).

Subjects with pre-existing cirrhosis who demonstrate a change in the Child-Pugh Score from A to B or C at any point in the study should also have their dosing modified per the appropriate dosing regimen. Changes in Child-Pugh Score that result from a transient, explainable change in laboratory parameters (eg, increase in vitamin K resulting in change in INR) should be documented appropriately and discussed with the Medical Monitor before any continuation or change to the dosing regimen (Appendix A).

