7.6. Dose Adjustment, Interruption, and Withdrawal from Investigational Product or Study

Investigational product may be temporarily decreased (eg, from 10 mg twice weekly to 5 mg twice weekly, or from 5 mg twice weekly to 5 mg once weekly) or temporarily or permanently stopped based on safety and/or tolerability concerns. Investigational product may be resumed at the maintenance dose upon resolution of gastroenteritis or worsening renal function or dehydration if there is no evidence of liver injury. For rechallenge, following all other dose interruptions (see Table 7), investigational product should be initiated at a lower dose and subjects monitored more frequently with up-titration considered based on tolerability.

Adjustments, interruptions, discontinuation, and any rechallenge of investigational product should be implemented per the criteria outlined in Table 7. Subjects who discontinue investigational product are expected to continue in the study (and follow the regular visit schedule) until the end of the study, and the study will terminate at the time when the needed number of adjudicated events has accrued. If a subject reaches an outcome event, he or she should continue the regular visit schedule and continue taking investigational product as long as the subject has not met any of the criteria for mandatory interruption of investigational product outlined in Table 7, and the Investigator assesses it as safe to continue. In general, subjects should be strongly encouraged to both stay on investigational product and remain in the study until study termination. If a subject discontinues investigational product and cannot continue to attend regularly scheduled study visits, the subject should be strongly encouraged to participate in study follow-up via phone calls or electronic medical record review as described in [Section 7.9](#).

Table 7: Criteria for Dose Adjustment, Interruption, Discontinuation and Rechallenge

DOSE ADJUSTMENT		
Criteria	Action Taken with IP	Adjustment
Progress to cirrhosis and have CP A cirrhosis (CP score <7)	Adjust to a maximum daily dose of 10 mg (or equivalent placebo) in a blinded fashion	Not applicable. Remain at maximum daily dose of 10 mg (or equivalent placebo) for remainder of study.

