Progress to CP B or C cirrhosis (CP score ≥7)	Adjust IP dose to 5 mg once weekly, then titrate to a maximum 10 mg twice weekly (at least 3 days apart).	After a minimum of 3 months, if at a lower dose, subjects may titrate to a maximum IP dose of 10 mg twice weekly per Investigator discretion.
New onset Severe Pruritus	Drug holiday or less frequent dosing	Return to original dose regimen if tolerated
DOSE INTERRUPTION		
Criteria	Action Taken with IP^a	Rechallenge^b
If liver biochemistries indicative of suspected hepatic injury are identified as exceeding upper threshold criteria and require immediate interruption (see Part A of Table 4) ^c	Interrupt immediately upon initial observation	Patient may be rechallenged after a minimum of 30 days if fully resolved OR stable and approved by the Medical Monitor and Investigator.

Table 7: Criteria for Dose Adjustment, Interruption, Discontinuation and Rechallenge (Continued)

Other liver biochemistries indicative of suspected hepatic injury are outside upper threshold criteria upon repeat testing as defined in Part A of Table 4 ^d	Interrupt after confirmation by repeat testing	
Liver biochemistries indicative of potential hepatic decompensation in the absence of symptoms (see Part B of Table 4) ^e	Closely monitor until normalization or stabilization. If values continue to increase relative to the baseline value, interrupt	
Clinical events indicative of hepatic decompensation (see Part B of Table 5)	Closely monitor until normalization	The subject may be rechallenged after a minimum of 30 days if fully resolved OR stable and approved by the Medical Monitor and Investigator. IP should be re-initiated at a lower dose (or lower dose frequency) and titrated per Investigator discretion.
Gastroenteritis (established severe abdominal pain, vomiting, diarrhea for more than 4 days)	Interrupt	If no evidence of liver injury is detected, IP may be restarted at the same dose after resolution of intercurrent illness.
Evidence of worsening of renal function or dehydration	Interrupt	
Pregnancy	Interrupt	Patient should continue with the study visit schedule. The subject may re-start IP when she is no longer pregnant or breastfeeding (if applicable) at the discretion of the Investigator and after discussion with the Medical Monitor
DOSE DISCONTINUATION		
Criteria	Action Taken with IP	Rechallenge

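### For a daily-dosed subject who newly develops Child-Pugh B or C cirrhosis, Section 7.4 reads as a step down to twice weekly, while Table 7 directs 5 mg once weekly

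*Protocol*

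**What the plan says.** Two current instructions cover a subject who becomes cirrhotic on study with Child-Pugh B or C.

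- **Section 7.4** says that dosing "should be down-titrated to the next lowest dosing frequency in the appropriate modified dosing regimen". It allows one exception, worded "unless the subject is currently taking a dose and frequency also specified in the modified dosing regimen"; this applies only where continuing at that dose is also judged clinically suitable by the Investigator. The sentence ends with a reference to Appendix A, not to Table 7. The preceding paragraph gives a general rule for any change in cirrhosis status or score: "Dosing should follow the titration schedule of the new dosing regimen".
- **Section 7.6, Table 7**, in the row for progression to Child-Pugh B or C cirrhosis, says: "Adjust IP dose to 5 mg once weekly, then titrate to a maximum 10 mg twice weekly". The cell beside it sets the timing of later steps: "After a minimum of 3 months, if at a lower dose, subjects may titrate to a maximum IP dose". The text of 7.6 says that adjustments "should be implemented per the criteria outlined in Table 7".

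Three other places bear on the question.

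- **Section 7.3** says that cirrhotic Child-Pugh B or C subjects "will follow a modified dosing regimen, initiating 5 mg OCA or matching placebo once weekly". That step lasts at least 3 months, then comes 5 mg twice weekly for at least 6 weeks, then at most 10 mg twice weekly. The Table 3 footnote in the same section ties the starting dose to status at Screening. Section 7.3 closes by sending sites to 7.4 and Appendix A, in a sentence that begins "Investigators should follow the dosing/titration schedule as shown described in".
- **Section 5.6** points to Sections 7.6 and 7.7 for the criteria for dosing adjustments.
- **Appendix A** words the once-weekly start for subjects who are B or C at Screening. It lists on-study progression as a reason to modify dosing, but its text gives no entry dose for it.

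**The concern.** The same clinical event leads to two different entry steps, depending on which section the site opens. The step in dispute is the lowest rung of the modified regimen. Section 5.5.2.2 describes that rung as the labelled starting dose in moderate and severe hepatic impairment, with adjustment only after tolerability at the lower dose is established.

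Safeguards elsewhere do not replace the rung. The Section 7.4.1 review of adverse events and laboratory results is required before a move to a higher dose, and the 1- and 2-month post-titration visits follow an up-titration. A subject who arrives at twice weekly by stepping down from daily dosing triggers neither. A subject who starts at once weekly triggers both on moving up to twice weekly. At stake is consistent dosing of hepatically impaired subjects in a blinded trial.

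**Working it through.** There is no plan figure to reproduce. The check is a side-by-side reading plus weekly-dose arithmetic.

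**Step 1: what 7.4 yields.** The modified regimen (Table 3, Table 13) has three rungs: 5 mg once weekly, 5 mg twice weekly and 10 mg twice weekly. It therefore has two frequencies. From daily dosing, the next lowest of them is twice weekly. The exception in 7.4 does not help, because neither 5 mg daily nor 10 mg daily is a rung of that regimen.

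**Step 2: what Table 7 yields.** For the same trigger the action is 5 mg once weekly.

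**Step 3: is there a tie-break?** Sections 5.6 and 7.6 assign dose adjustment to 7.6 and Table 7. Section 7.3 assigns the titration schedule to 7.4 and Appendix A. No sentence ranks one above the other.

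**Step 4: weekly dose = mg per dose × doses per week.**

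| Regimen | Calculation | mg/week |
|---|---|---|
| 10 mg daily | 10 × 7 | 70 |
| 5 mg daily | 5 × 7 | 35 |
| Table 7 entry | 5 × 1 | 5 |
| 7.4 entry, 5 mg tablet | 5 × 2 | 10 |
| 7.4 entry, 10 mg tablet kept (assumption) | 10 × 2 | 20 |

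The ratio of 7.4 entry to Table 7 entry is 10/5 = 2. It is 20/5 = 4 only if a subject on 10 mg daily is assumed to keep the 10 mg strength, which 7.4 does not say.

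**Step 5: size of the cut from daily dosing, assuming tablet strength is not raised.**

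- From 70 mg/week under 7.4: (70 − 10)/70 = 86%, or (70 − 20)/70 = 71% if the 10 mg tablet is kept.
- From 70 mg/week under Table 7: (70 − 5)/70 = 93%.
- From 35 mg/week under 7.4: (35 − 10)/35 = 71%.
- From 35 mg/week under Table 7: (35 − 5)/35 = 86%.

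**Step 6: cumulative dose over the skipped step.** Taking the 3-month minimum as 13 weeks, Table 7 gives 5 × 13 = 65 mg and 5 mg twice weekly gives 10 × 13 = 130 mg.

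**Step 7: who is not affected.** For pre-existing cirrhosis moving from Child-Pugh A to B or C, 7.4 names no step and Table 7 supplies the dose, so there is no conflict. A subject on 5 mg twice weekly who steps down under 7.4 reaches 5 mg once weekly, the same as Table 7.

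**The case against.** The strongest reply is that the protocol already shows which section governs. Sections 5.6 and 7.6 both place adjustment criteria in 7.6, and Table 7 names this exact trigger with a dose in milligrams. Section 7.4 never uses the words twice weekly, and its general rule about the new regimen's titration schedule fits entry at the first rung. This has weight: the balance of the text favours Table 7. It does not remove the conflict. The specific step-down sentence in 7.4 follows the general one and says something different, it refers to Appendix A and not to Table 7, and 7.3 sends sites to 7.4.

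The reply also limits the point in ways that should be accepted. Section 7.3 is only supporting evidence for on-study progressors, given the Screening wording in the Table 3 footnote and Appendix A. The Appendix A flowchart (Figure 3) is not visible in the copy reviewed, so the statement that Appendix A gives no entry dose holds for its text only. Investigators may lower dose or frequency at any time. Subjects with a listed laboratory trigger or decompensation event fall under the rules of Tables 4 and 5, so the conflict bites on those who reach B or C without one. The document gives no count of them.

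A reader might infer that twice-weekly entry has been shown to be harmful, from the post-marketing cases in Section 5.7. The documents do not support that. Those cases involved up to 7 × 5 = 35 mg/week, and the sponsor's initial assessment found insufficient evidence of a causal link with the higher dosing. They do not settle 5 versus 10 mg/week.

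**Conclusion.** The inconsistency is real and confined to 7.4 against Table 7, for subjects on 5 or 10 mg daily who newly develop Child-Pugh B or C cirrhosis. Its supportable size is a 2-fold difference in entry dose (10 against 5 mg/week) and the loss of the once-weekly tolerability step. This rests on reading the next lowest frequency after daily as twice weekly, and on use of the 5 mg tablet.

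A reader might infer a 4-fold difference (20 mg/week), but that needs the further assumption that the 10 mg strength is kept. A reader might also infer that a dose cap is breached or that efficacy is biased. Neither follows. Both routes stay at or below 10 mg twice weekly, and Section 13.1 analyses efficacy by randomised treatment. The point is a minor-to-moderate safety consistency fix.

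**What to change.** In Section 7.4, replace the step-down wording for daily-dosed subjects with: *adjusted to 5 mg once weekly and then titrated per Table 7 and Section 7.3, each step up subject to Section 7.4.1*. Add a cross-reference from 7.4 to Table 7. In Appendix A, state the same entry dose for on-study progressors, and check that Figure 3 agrees. The reference to 7.3 also supplies the intermediate 5 mg twice-weekly rung, which Table 7 does not name.

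The 7.4 exception for subjects already on a modified-regimen dose can stay, as can the Table 7 qualifier about being at a lower dose. Reconciling the rule for daily-dosed subjects does not require removing investigator judgement from either. Table 7 should not be aligned to 7.4, because that would remove the once-weekly start.

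The cost is one sentence in 7.4 and one line in Appendix A, by amendment or clarification letter, plus a check that interactive web response system (IWRS) dispensing matches. Sample size, endpoints and analysis do not change.

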7.4.1. Pre-Titration Tolerability Assessment Requirements

Tolerability of investigational product must be assessed prior to titrating a subject to a higher dose. A review of adverse events and safety laboratory results (eg, chemistry, hematology, and coagulation) obtained within 2 months of the up-titration visit must be performed as part of the investigational product tolerability assessment, prior to any planned up-titration in investigative product (eg, Month 3, Month 6). Safety laboratory results obtained at the Month 1 visit (for titration at Month 3) or at the Post-Titration Assessment visits (for titration prior to or at the

subsequent quarterly visit) are acceptable for review purposes; however, if for any reason, laboratory results are not available at the time of the planned up-titration visit, additional laboratory samples must be obtained and reviewed, prior to up-titrating the subject to a higher dose.

To be eligible for a dose up-titration:

- Subjects should not be experiencing significant AEs that are suspected to be related to investigational product (eg, severe pruritus) or displaying other symptoms that may indicate intolerability of investigational product.
- There must be no clinically significant increase (as determined by the Investigator) in the subject's liver function tests.

7.5. Monitoring and Management of Potential Hepatic Injury and/or Disease Progression

Given the chronic nature of PBC, it is important to monitor for potential hepatic injury, disease progression and/or hepatic decompensation. Child-Pugh and MELD scores will be reviewed at each visit where labs are drawn ([Table 1](#)). Child Pugh Scores should only be applied in patients who have evidence of cirrhosis at screening or demonstrate evidence of cirrhosis at screening or progression to cirrhosis during the study based on criteria presented in [Section 7.5.4](#). In addition, adverse events, signs and symptoms of potential hepatic injury or decompensation, and laboratory values will also be reviewed at regular intervals as described in [Section 7.1.1](#). Based on the assessments of signs and symptoms of hepatic injury and liver biochemistry, the investigational product may be interrupted or discontinued per criteria discussed in [Section 7.5.2](#) and [Section 7.5.3](#), and close monitoring procedures will be implemented ([Section 7.7](#)).

7.5.1. Signs and Symptoms of Hepatic Injury or Decompensation

Subjects should be instructed to contact study personnel if they notice any of the following signs and symptoms or have healthcare interactions outside of the study setting.

Signs and Symptoms of Hepatic Injury or Decompensation:

- Specific signs and symptoms of liver impairment: eg, yellowing of the skin or the whites of eyes, pale-colored stools, urine color change from pale to deep amber [dark] (reflecting impaired bilirubin metabolism)
- More general signs and symptoms of ascites and encephalopathy: eg, confusion, swelling of the legs or abdomen
- Non-specific signs and symptoms of impaired health: eg, nausea, vomiting, abdominal pain, diarrhea, weight loss, fever and chills, worsening or new fatigue, weakness, loss of appetite
- Significant intercurrent illnesses such as gastroenteritis may exacerbate hepatic injury or decompensation (eg, established severe abdominal pain, vomiting, and diarrhea for more than 4 days) and should be an indication for prompt investigational product interruption and complete subject evaluation

Other Symptoms:

- Worsening of renal function or likely dehydration

Healthcare Provider (HCP) Interactions:

- Visits to primary HCP or referral to any specialist for any new symptoms (other than ongoing care for stable comorbidities)
- New medications or changes to current medications prescribed from HCP or any new over the counter medications or herbal supplements
- Laboratory procedures or assessments performed by an HCP

Signs and symptoms for potential hepatic injury or decompensation should be followed by (1) evaluation of liver biochemistry for suspected drug-induced liver injury (DILI) or potential hepatic decompensation (Section 7.5.2), (2) assessment of clinical events for potential hepatic decompensation (Section 7.5) (3) triggering of investigational product interruption or discontinuation per criteria (Section 8.4), (4) documentation in the AE eCRF or the SAE eCRFs (Section 12.1.5.1 and Section 12.1.5.2), and (5) contact with the Medical Monitor.

7.5.2. Liver Biochemistry Assessments for Suspected Hepatic Injury or Potential Hepatic Decompensation

Liver biochemistry will be assessed to evaluate biochemical triggers that will prompt an immediate reevaluation of subjects for potential hepatic injury or hepatic decompensation.

[figure not shown]
These assessments will be performed at:

- Each protocol-specified visit (Table 1)
- Unscheduled visits as needed in the event of signs or symptoms of suspected hepatic injury or decompensation or if laboratory alerts have been triggered

It is important that the laboratory assessments be completed as required and that the central laboratory be used for assessments whenever possible. In the event that a subject cannot return to the clinic for a scheduled or unscheduled visit, or there is an event that triggers a need for an immediate assessment, the use of a local lab is permissible at the discretion of the Investigator. In these cases, the Investigator will obtain the laboratory results and the laboratory normal ranges.

The process for assessing criteria is presented in Figure 2, and the specific threshold(s) for each laboratory analyte to trigger mandatory repeat testing and, potentially a complete subject evaluation (depending on the repeat result) are summarized in Table 4.

Figure 2: DILI Management Algorithm

DILI = drug-induced liver injury; IP = Investigational Product

Note: Other laboratory criteria include: ALT, AST, total bilirubin, INR, and electrolytes (sodium).

Table 4: Liver Laboratory Criteria for Monitoring of Suspected Hepatic Injury or Potential Hepatic Decompensation and Criteria for Interruption or Discontinuation of Investigational Product

A. Laboratory Criteria for Monitoring Suspected Hepatic Injury		
Laboratory Parameter	Action Taken	Rechallenging Criteria
Total Bilirubin		If a subject interrupts IP, they may be rechallenged after a minimum of 30 days if fully resolved OR stable and approved by the Medical Monitor and Investigator.
Baseline \leq ULN and \geq 3x baseline	Interrupt IP	
Baseline $>$ ULN and \geq 2x Baseline	Interrupt IP	
ALT or AST		
$>$ 3x baseline (and $>$ ULN)	Interrupt IP	
\geq 2x baseline	Repeat Test in 2 to 3 days, interrupt IP if still elevated	
Electrolytes^a		
Sodium $<$ 130 mEq/L	Repeat Test in 2 to 3 days, interrupt IP if still below threshold	
B. Laboratory Criteria for Monitoring Potential Hepatic Decompensation (Absence of Clinical Symptoms)		
Total Bilirubin	Closely monitor until normalization or stabilization.	The subject may be rechallenged after a minimum of 30 days if fully resolved OR stable and approved by the Medical Monitor and Investigator.
Baseline \leq ULN and 1.5 mg/dL increase from baseline Baseline $>$ ULN and 1.0 mg/dL increase from baseline	If values continue to increase relative to the baseline value, interrupt IP.	If laboratory values do not normalize, IP should not be restarted.
INR^b		
$>$ 0.3unit increase from baseline	Closely monitor until normalization or stabilization. If values continue to increase relative to the baseline value, interrupt IP.	The subject may be rechallenged after a minimum of 30 days if fully resolved OR stable and approved by the Medical Monitor and Investigator. If laboratory values do not normalize, IP should not be restarted.
\geq 2.0 unless due to vitamin K deficiency	Discontinue IP permanently	Continue to return for scheduled study visits for safety follow up. Monitor closely for clinical outcomes per protocol.
C. Laboratory Criteria for Monitoring Potential Hepatic Decompensation in the Presence of Clinical Symptoms		
Total bilirubin thresholds defined in Part B OR an INR increase from baseline of \geq 1.5 are observed in the presence of clinical symptoms of cholestatic hepatitis or hepatic encephalopathy ^c	Discontinue IP permanently	Continue to return for scheduled study visits for safety follow up. Monitor closely for clinical outcomes per protocol.

IP = investigational product

^a Sodium will be measured as an assessment of liver failure (hyponatremia).

^b Does not apply in subjects on anti-coagulants.

^c Symptoms of cholestatic hepatitis includes dark urine and jaundice. Symptoms of hepatic encephalopathy may include lack of awareness, shortened attention span, lethargy, gross disorientation, or coma (unresponsive to verbal or noxious stimuli)

It should be noted that it is difficult to recognize every potential marker of hepatic or renal deterioration. There is no substitute for good medical judgment. Investigators will be reminded to be cautious and mindful in their evaluation of subjects' symptoms, signs, and laboratory results. However, for example, a single abnormal laboratory analyte result may be artefactual; accordingly, Investigators will be allowed to implement an alternate follow-up procedure if

considered appropriate based on their medical judgement but only after documented agreement with the Sponsor's Medical Monitor.

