If INR increases ≥ 2.0 in absence of clinical symptoms criteria (unless due to vitamin K deficiency)	Discontinue / No Rechallenge	Discontinue IP permanently and continue to return for scheduled study visits for safety follow up. Monitor closely for clinical outcomes per protocol. Continue to return for scheduled study visits for safety follow up. Monitor closely for clinical outcomes according to protocol assessments.
If total bilirubin, thresholds (Part B of Table 4) are observed in the presence of clinical symptoms of cholestatic hepatitis or hepatic encephalopathy ^f		
Multi-Organ failure requiring hospitalization		
Liver transplantation		

Fully resolved = Return to baseline levels or return to within normal limits (WNL). IP = investigational product

^a If subject is unable to be evaluated promptly, study drug must be immediately interrupted.

^b Requires complete documentation of complete resolution or normal/baseline results based on laboratory parameters and symptoms.

^c Total bilirubin baseline \leq ULN and Postbaseline $\geq 3x$ baseline, Baseline $>$ ULN and Postbaseline $\geq 2x$ Baseline, ALT or AST $> 3x$ baseline (and $>$ ULN)

^d ALT or AST $\geq 2x$ baseline, albumin < 3.2 g/L or electrolytes (sodium < 130 mEq/L).

^e Conjugated bilirubin > 0.5 mg/dL increase from baseline; Total bilirubin Baseline \leq ULN and 1.5 mg/dL increase from baseline OR Baseline $>$ ULN and 1.0 mg/dL increase from baseline; INR > 0.3 increase from baseline

^f If INR increases ≥ 2.0 in the absence of clinical symptoms or if conjugated bilirubin or total bilirubin, thresholds OR an INR increase from baseline of ≥ 1.5 are observed in the presence of clinical symptoms of cholestatic hepatitis or hepatic encephalopathy.

^g Multi organ failure including hepatorenal syndrome Type 1 or Type 2 and acute kidney injury, hepatopulmonary syndrome, or portopulmonary syndrome.

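### Table 4 Part B both permits and forbids restarting drug when bilirubin or INR is stable but not normalized; Table 7 repeats the conflict, and its footnotes carry an albumin unit error and unmatched conjugated bilirubin criteria

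*Protocol*

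**What the plan says.** **Table 4 Part B (Section 7.5.2)** covers rises in total bilirubin or INR without symptoms. The action cell reads "Closely monitor until normalization or stabilization", with interruption if values keep rising. The rechallenge cell, for bilirubin and for INR alike, has two sentences. The first is "The subject may be rechallenged after a minimum of 30 days if fully resolved OR stable and approved by the Medical Monitor and Investigator". The second is "If laboratory values do not normalize, IP should not be restarted".

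**Table 7 (Section 7.6)** restates the rules. Its rechallenge text for liver biochemistry reads "Patient may be rechallenged after a minimum of 30 days if fully resolved OR stable and approved by the Medical Monitor and Investigator". Footnote b, attached to the Rechallenge column heading, reads "Requires complete documentation of complete resolution or normal/baseline results based on laboratory parameters and symptoms". A note under the table defines full resolution as a value back at baseline or inside the normal range.

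**Which section governs what.** Section 7.5 says that "the investigational product may be interrupted or discontinued per criteria discussed in" Sections 7.5.2 and 7.5.3. Section 7.6 says: "Adjustments, interruptions, discontinuation, and any rechallenge of investigational product should be implemented per the criteria outlined in Table 7".

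**Other Table 7 footnotes.** Footnote d includes albumin below 3.2 g/L among the triggers for interruption after a repeat test. Footnote e includes a conjugated bilirubin rise above 0.5 mg/dL among the values to monitor and, if rising, to interrupt on. Footnote f includes conjugated bilirubin among the grounds for permanent discontinuation when symptoms are present.

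**The concern.** These are the rules for stopping and restarting drug in subjects with possible liver injury, and the protocol presents its laboratory monitoring as rules-based (Section 5.6). For a bilirubin or INR that has stopped rising but has returned neither to baseline nor to normal, the investigator and Medical Monitor find permission to restart and an instruction not to restart in the same cell. Two similar subjects could be handled differently, with each decision defensible from the text. The footnote discrepancies have the same character: one trigger that will never operate as printed, and one analyte that can lead to a permanent stop in a footnote but does not appear in the table the row refers to.

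**Working it through.** The protocol states no figure to reproduce here. The check is a side-by-side reading plus a unit conversion.

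**1. Can *stable* be read as *normalized*?** No. The Part B action cell offers normalization and stabilization as alternatives. Table 7's definition of full resolution already covers return to baseline and return to normal, so the extra word *stable* must cover values that are neither. The second sentence of the Part B cell then excludes those values.

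**2. Example (assumed baseline total bilirubin 2.0 mg/dL).**
- The Appendix C upper limit is 1.2 mg/dL. Entry is allowed up to 5 × 1.2 = 6.0 mg/dL, so this baseline is eligible.
- Baseline is above normal, so Part B starts at 2.0 + 1.0 = 3.0 mg/dL and Part A at 2 × 2.0 = 4.0 mg/dL.
- Drug is interrupted at 3.2 mg/dL and rising. After 30 days the value is steady at 2.5 mg/dL, above both baseline (2.0) and the upper limit (1.2).

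| Text | Restart at a steady 2.5 mg/dL? |
|---|---|
| Table 4 Part B, first sentence | Allowed with approval |
| Table 4 Part B, second sentence | Not allowed |
| Table 7 rechallenge cell (if it spans the Part B row) | Allowed with approval |
| Table 7 footnote b (read as a requirement) | Not met |

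**3. Does precedence settle it?** Section 7.6 assigns rechallenge to Table 7; the Section 7.5 sentence concerns interruption and discontinuation only. Following Table 7 still leaves its cell against its footnote b. Table 4 Part A also allows restart on a stable value, without the normalization sentence, so footnote b read strictly conflicts with Part A as well.

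**4. Albumin.** 1 g/dL = 10 g/L, so 3.2 g/L = 0.32 g/dL.
- Against the lower reference limit of 33 g/L (Appendix C, ages 18 to 69): 3.2 / 33 = 0.097.
- Against the bound of the worst Child-Pugh albumin class, 28 g/L (Table 6): 3.2 / 28 = 0.11.
- If g/dL was meant: 32 / 33 = 0.97, just below the reference limit, which is plausible.

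The other items in footnote d (ALT or AST at twice baseline, sodium below 130 mEq/L) match Table 4 Part A. Albumin is the only one with no counterpart there, and the note under Figure 2 omits it too.

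**5. Conjugated bilirubin.** The total bilirubin and INR items in footnote e match Table 4 Part B; conjugated bilirubin is the extra. Table 4 Part C and the Table 7 discontinuation row name total bilirubin, not conjugated. Footnote f gives no conjugated threshold. If it borrows footnote e's 0.5 mg/dL and unconjugated bilirubin is unchanged, the total rises by the same amount as the conjugated fraction. The band where footnote f stops drug permanently but Part C's bilirubin criterion is not met is then 1.5 − 0.5 = 1.0 mg/dL wide (baseline at or below the upper limit) or 1.0 − 0.5 = 0.5 mg/dL wide (baseline above it). Section 7.7 requires both conjugated bilirubin and albumin at close-observation visits, so sites will hold these results.

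**The case against.** **The two tables do not oppose each other on restart.** A reader might infer that Table 4 says no where Table 7 says yes. They carry almost the same permissive sentence. The conflict lies inside the Part B cell and again inside Table 7. Nor can it be said that neither table governs: Section 7.6 names Table 7 for rechallenge.

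**Table 7's coverage of Part B is an inference.** In the text available, the Table 7 row citing Part B has no rechallenge wording of its own; it appears to share a merged cell with the rows above. That needs checking against the original layout. The Part B conflict stands either way.

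**Footnote b has a milder reading.** It sits on a column that also covers gastroenteritis and pregnancy, and could be a documentation rule for the fully resolved route only. On that reading Table 7 is consistent. But the footnote is not limited in that way, and Part B still contradicts itself.

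**Return to a raised baseline.** A reader might infer that a subject back at a baseline above the upper limit is barred because the value is not normal. The documents do not support this: Part B permits restart on full resolution, and Table 7 defines that to include return to baseline.

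**Harm is limited.** No site restarts alone. Thirty days and approval by the Medical Monitor and Investigator are required, and Section 7.6 calls for a lower dose and more frequent monitoring. Section 7.5.2 also allows an alternate follow-up procedure after documented agreement with the Medical Monitor. All of this stands, but none of it tells the approvers which criterion is the default.

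**The footnotes are secondary text.** The table rows agree on total bilirubin, footnote f errs toward stopping drug, and worsening synthetic function is covered in Table 5. The bands above rest on a borrowed threshold and are not protocol facts. The mismatch itself is.

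**Conclusion.** The point holds as an inconsistency in the stop and restart rules. Table 4 Part B contradicts itself for bilirubin and INR values that are stable but neither at baseline nor normal. Table 7 repeats the conflict between its cell and footnote b, provided the cell spans the Part B row and footnote b is read as a requirement. The albumin trigger is a unit error that cannot fire in practice and has no counterpart in Part A. Conjugated bilirubin appears in footnotes e and f but not in Table 4 Parts B and C or the Table 7 rows.

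How many subjects would be interrupted under Part B and then stabilize without resolving is not stated, and no count is offered. The consequence is for dosing safety and consistency across sites, limited by the approval step and lower-dose restart. A reader might infer damage to power or to the primary comparison; nothing in the documents supports that. It should be corrected because the rules concern liver safety and the correction is cheap.

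**What to change.** - **Restart.** State one rule for Table 4 Part B. One option is to restart only on return to baseline or to within normal limits, using Table 7's definition of full resolution, and to delete the stable alternative there. Make the Table 7 cell and footnote b say the same for Parts A and B. The liver-failure line in Table 5 Part B points to Table 4 Part B and also allows restart when stable, so check it against the chosen rule.
- **Albumin.** Correct to 3.2 g/dL (32 g/L) and add it to Table 4 Part A, or delete it from footnote d.
- **Conjugated bilirubin.** Add it to Table 4 Parts B and C with an explicit threshold for each action, or delete it from footnotes e and f.

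The clinical team should choose the values. The cost is a protocol clarification and a letter to sites; no new procedures or samples are needed.
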